### Objectives

The primary objective is to assess the effectiveness of training a clinician to be a 'value champion' within their clinical setting to decrease the use of three classes of potentially inappropriate prescription medications (PIMs) among people living with dementia.

(PLWD) Secondary objectives include determining if the intervention is associated with a reduction in emergency department (ED) visits or hospitalizations due to a fall, and examining five implementation outcomes: appropriateness, feasibility, fidelity, penetration, and equity.

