## **2 ADDITIONALLY, DATA COLLECTED THROUGH TWO INTERVIEWS WITH APPROXIMATELY 8 CLINICIAN VALUE CHAMPIONS WILL PROVIDE US WITH THE MEASURES WE NEED TO ASSESS FIVE IMPLEMENTATION OUTCOMES: APPROPRIATENESS, FIDELITY, FEASIBILITY, PENETRATION AND EQUITY.**

### **BACKGROUND AND RATIONALE**

#### **2.1 Background on Condition, Disease, or Other Primary Study Focus**

For people living with dementia (PLWD) the overuse of Potentially Inappropriate Medications (PIMs), those for which the potential for harm outweighs benefit, remains a persistent problem despite evidence-based guidelines supporting their de-adoption. A group of geriatric experts convened by the Choosing Wisely initiative identified three classes of PIMs for PLWD: antipsychotics, benzodiazepines, and hypoglycemics (sulfonylureas and insulin) with adequate glycemic control. In a systematic review the prevalence of PIMs when cognitive impairment was reported ranged from 20.6% to 80.5%. Approximately 14.3% of Medicare Part D enrollees with dementia residing in the general community are prescribed an antipsychotic. The prevalence of potentially inappropriate benzodiazepine prescriptions has been reported to be as high as 20% among elderly persons with dementia living in the community. The proportion of elderly patients with an A1c < 7% who received a prescription for sulfonylurea, insulin or combined insulin and sulfonylurea therapies was 35.2%, 24.2% and 16.3% respectively and was as prevalent in those with dementia as in those without. Park and colleagues compared rates of prescribing low-value medications in the elderly from 2006-2015 in both traditional Medicare and Medicare Advantage. Not only was there no difference in rates between the two groups, there was also no evidence of any decline in rates of prescribing over time, including use of benzodiazepines in PLWD.

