#### 9.2.1 Treatment Assignment Procedures

The unit of randomization will be the primary care practice or team. We anticipate 32 out of 39 teams from USMM to meet eligibility and 26 out of 28 practices for Ochsner. Within each ACO, we will randomly select half of the practices for participation in the value champion training and the remaining practices will continue with care as usual. Prior to random assignment, we will stratify practices based on high versus low historic prescribing rates. We will select practices for randomization and inclusion using a cut-point based on the distribution of overall rates for all 3 therapeutic classes using data for 2019-2020. Once randomized, a clinician value champion will be recruited from each of the clinics randomized to the intervention arm of the study in partnership with the ACO leadership.

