#### 9.4.2 Secondary outcomes

As a secondary outcome, for Specific Aim #2, we will also assess the incidence of falls during the study window. Falls are difficult to monitor using claims data, but Min and colleagues have developed a method that IAC and Brandeis staff (Co-Investigator [name]) have helped test for ICD-10. We will use the most conservative definition that looks for the presence of fall ‘reason for visit’ code on ED, ambulatory, or inpatient visit as indicated by a clinician bill (Part B). Key covariates in all of our regression models will include age and sex, both derived from the Medicare beneficiary summary files, house at IAC.

For Specific Aim #3, the five important implementation outcomes: appropriateness, fidelity, feasibility, and penetration will be assessed by analyzing interviews with clinician value champions. The Clinician interviews will provide us with data we need to assess the implementation outcomes.

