### 9.5 Data Analyses

Following an intent-to-treat design, all Medicare beneficiaries meeting our dementia eligibility criteria will be included in the study, regardless of level of engagement with practice clinicians. Data analysis will begin with descriptive statistics, comparing the mix of patients at each practice including demographics, chronic conditions, and incident versus prevalent dementia. This will allow us to check for balance between treatment and control practices and inform subsequent modeling. To determine the impact of the intervention, we will construct hierarchical models with time period observations nested within patient. These models will be random effects or generalized estimating equations (GEE) with robust standard errors, and will be either linear, if original MPRs are used as outcome, or generalized linear, if transformation necessary. The key variable of interest in these models will be the treatment indicator (assigned based on practice). Since there could well be a time effect of treatment, we will explore several model specifications, such as discrete indicators for the time periods or a single continuous variable. Interactions of treatment with time period will also be explored. By examining various different specifications involving time, we should be able to determine whether the intervention leads to a one-time change, a gradual trend over time, or a combination of both (an immediate jump with a further change, as time passes). Finally, we will explore the impact of this intervention on health inequities by stratifying our primary analysis by race/ethnicity.

Specific to Aim #3: Current approaches to evaluating implementation outcomes are still nascent, with few measures that have validated psychometric properties. Conceptually, these measures are inter-dependent, and are connected with service outcomes, such as patient safety. We will use data collected from interviews with the Value Champions to conduct a thematic analysis of the five implementation outcomes using a deductive approach.

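### Aim 2 compares falls only across the whole dementia cohort; the contrast is unbiased but diluted, and pre-training claims that could sharpen it are not used

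*Combined protocol and SAP*

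**What the plan says.** The Précis sets the fall objective as "determining if the intervention is associated with a reduction in emergency department (ED) visits or hospitalizations due to a fall", and section 1.2 repeats it. The only analysis set is in section 9.5: "all Medicare beneficiaries meeting our dementia eligibility criteria will be included in the study, regardless of level of engagement with practice clinicians". Eligibility in sections 4.1 and 4.2 turns on a visit, Medicare coverage, a dementia diagnosis, and no metastatic cancer or hospice. Use of a target drug is not required.

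On covariates, section 9.4.2 states: "Key covariates in all of our regression models will include age and sex". Section 9.5 leaves room for more. It first describes the patient mix, including chronic conditions and incident versus prevalent dementia, and adds: "This will allow us to check for balance between treatment and control practices and inform subsequent modeling". The one stratified patient analysis concerns the primary outcome: "we will explore the impact of this intervention on health inequities by stratifying our primary analysis by race/ethnicity". Prescribing history enters at practice level only (section 9.2.1): "We will select practices for randomization and inclusion using a cut-point based on the distribution of overall rates for all 3 therapeutic classes".

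No analysis named for Aim 2 uses a patient's drug use or falls before training. Section 9.2 gives power for the medication possession rate (MPR) only. No fall rate, expected fall effect or fall power appears.

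**The concern.** The study rationale and section 7.1 attribute fall harm to these drugs, so the expected route to fewer falls is less exposure. A patient with no target drug before training can benefit only through a new start that is avoided. The falls of all other non-users add variance without adding effect.

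If MPR dropped exactly as hypothesised and the drugs do cause falls, the whole-cohort comparison could still easily miss it. That null would not separate an intervention that does not prevent falls from a contrast with too little information. The claims files can show who held a target drug, who had already fallen, and how often each practice's patients had fall claims, all before training. A user analysis chosen after the result is known would look like a search through subgroups.

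**Working it through.** **The plan's own figure.** Power = Φ(d × √(n/2) − 1.96), with d in SD units. For 1,600 per group and d = 0.10 it is 80.7%; for 6,400 and 0.10, 99.99%; for 6,400 and 0.05, 80.7%. The MPR statements in section 9.2 reproduce (two-sided 5%). Nothing comparable exists for falls.

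**Share of users (section 2.1).** "Approximately 14.3% of Medicare Part D enrollees with dementia residing in the general community are prescribed an antipsychotic"; benzodiazepine use is given as up to 20%. The share using either drug is:
- fully nested: 20%
- independent: 1 − 0.857 × 0.80 = 31.4%
- disjoint: 34.3%

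The hypoglycemic figures apply only to patients with A1c below 7%. If that group is assumed to be 20% to 40% of the cohort, any-class use runs from about 20% (nested) to 65% (disjoint).

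**Exposure cut at the plan's target of 0.10 SD per class.** Treating MPR as roughly 0/1, the cut is 0.10 × √(p(1−p)):
- antipsychotics: 0.10 × √(0.143 × 0.857) = 3.5 points
- benzodiazepines: 0.10 × √(0.20 × 0.80) = 4.0 points
- hypoglycemics: 4 points (assumed)

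The total is about 11.5 points of patient-time.

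**Fall contrast.** From the documents: 2,500 patients per arm, 32 + 26 = 58 practices, m = 5,000/58 = 86.2 per practice. Assumed: yearly off-drug fall risk R0 of 10% or 20%; risk ratio on drug (RR) of 1.5 or 2.0; users f = 34% or 45% of the cohort; ICC 0.005 or 0.02; the whole cut in existing users. That makes 16 corner scenarios.

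- Whole-cohort difference = 0.115 × R0 × (RR − 1). User difference = that / f.
- SE = √[2R(1−R)/n × (1 + (m−1) × ICC)]. Whole cohort: R = R0(1 + f(RR−1)). Users: R = R0 × RR, with n and m multiplied by f.

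One scenario in full (R0 = 20%, RR = 1.5, f = 34%, ICC = 0.005):
- Whole cohort: difference 0.115 × 0.20 × 0.5 = 1.15 points; R = 0.234; design effect 1 + 85.2 × 0.005 = 1.426; SE = √(2 × 0.234 × 0.766/2,500 × 1.426) = 1.43 points; power 13%.
- Users: difference 1.15/0.34 = 3.38 points; R = 0.30; n = 850; m = 29.3; design effect 1.142; SE = √(2 × 0.30 × 0.70/850 × 1.142) = 2.37 points; power 30%.
- Signal-to-noise ratio: (3.38/2.37)/(1.15/1.43) = 1.77.

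| Over the 16 scenarios | Whole cohort | Pre-training users |
|---|---|---|
| Difference, points | 0.6 to 2.3 | 1.3 to 6.8 |
| SE, points | 1.1 to 2.1 | 1.6 to 3.0 |
| Power | 7% to 34% | 10% to 76% |

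The signal-to-noise gain is 1.4 to 2.1 times. User power is below 50% in 13 of the 16 scenarios.

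**Sensitivity.**
- With users at 55% to 65% of the cohort, the gain is 1.2 to 1.5 times.
- The gain is lost when the share of the cut from avoided new starts reaches 1 − 1/gain. Unrounded gains of 1.44 to 2.08 give 30% to 52%. At 55% to 65% users, gains of 1.22 to 1.52 give about 18% to 34%.
- If 30% of the cut comes from new starts (users 34% to 45%), the gain is 1.0 to 1.5 and user power 7% to 46%.
- A second set of assumptions (fall rate 10% to 30%, risk ratio for intervention versus control among users 0.8 or 0.9, ICC 0 to 0.02, users 20% to 57%) gives power of 4% to 77% in the whole cohort and 7% to 95% in users. The whole cohort never reaches 80%.
- At a 20% fall rate and ICC 0.01, the smallest whole-cohort risk ratio detectable with 80% power is 0.793. That needs 1 − 0.207/0.314 = 0.34 among users at 31.4%, or 1 − 0.207/0.5 = 0.59 at 50%.

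**The case against.** The strongest reply is that nothing here is an error. The objective asks about the intervention's effect on falls, and an intent-to-treat contrast between randomised practices answers it without bias. Section 9.1 describes a demonstration project, section 10.1 treats falls as exploratory, and no fall power is claimed. This stands: the whole-cohort analysis should stay, and the point is about information.

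It is also fair that the user analysis is no cure. It is below 50% power in most scenarios. The best case (6.8 points, 76%) is generous: a 4-point cut in the third class implies about 20% use, and independence then gives f = 1 − 0.857 × 0.80 × 0.80 = 45%. Reaching 34% needs heavy overlap between classes, yet the cuts are summed as though there were none. Training also lasts six months before the 12-month project, so some users will have stopped and others started by then.

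Three stronger readings are tempting, and the documents support none of them:
- **A whole-cohort null is nearly assured, or the effect is lost altogether.** Even the assumed range leaves up to 34% power, and every fall input is an assumption.
- **Most patients hold no target drug.** This is likely for antipsychotics and benzodiazepines, but the any-class share is not given, and selecting practices on historic prescribing could raise it.
- **The short covariate list causes the dilution.** It does not; the analysis population does. Adding baseline use as a main effect would not remove it. The list is also open-ended, and the balance checks may extend it.

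**Conclusion.** The point holds as a modest improvement to a secondary outcome. The whole-cohort fall contrast is valid, diluted and probably weak: about 7% to 34% power under the main assumptions, so a null is likely and uninformative. A contrast in pre-training users carries about 1.4 to 2.1 times the signal-to-noise if users are 34% to 45% of the cohort and the whole exposure cut falls on them. It carries 1.2 to 1.5 times if they are 55% to 65%. It carries no advantage once avoided new starts supply roughly 30% to 52% of the cut, or less than that where users are more common. The direction rests on the plan's own mechanism. The sizes rest on an assumed fall rate, risk ratio, ICC, user share and third-class cut. The gain from adjusting for earlier falls was not quantified; it depends on how well past falls and practice coding predict later falls.

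**What to change.** In section 9.5, keep the whole-cohort intent-to-treat fall analysis and add two items for Aim 2:

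1. Adjust the fall models for any fall claim in the 12 months before champion training and for the practice's fall rate over the same period. This needs only claims already held. Use the same fall definition as for the outcome, after reconciling the Précis and section 1.2 (emergency department visits or hospitalizations) with sections 3 and 9.4.2 (which also count ambulatory visits).
2. Prespecify a supplementary fall analysis in patients with a target-class fill in the last quarter before training, by arm as randomised and with clustering by practice. This group is fixed before the champions act, so the randomised comparison is kept.

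The cost is SAP wording and some programming. The user analysis has fewer patients, will often still be underpowered, and misses falls prevented through avoided new starts; the retained whole-cohort result covers those. Stating that a null fall result will be reported by its confidence interval is optional reporting advice.

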### Design and Outcomes

This study is a pragmatic cluster-randomized trial to test the effectiveness of a primary care clinician value champion for de-implementing potentially inappropriate medications among patients 65 years of age and older with a diagnosis of dementia. Medicare Part D pharmacy claims data will be analyzed at the end of the 12-month intervention for the primary outcome, the medication possession rates (MPR) for three groups of potentially inappropriate medications: antipsychotic medications, benzodiazepines, and hypoglycemic medications (sulfonylureas and insulin). In a similar fashion, a hospital admission, or an emergency department visit for a fall will be assessed at the end of the intervention using Medicare claims data. Finally, the five implementation outcomes – Appropriateness, Fidelity, Feasibility, Penetration and Equity - will be evaluated through analysis of interviews conducted with participating clinician value champions.

### Interventions and Duration

Primary care clinics within each of the two participating ACOs will be randomized to either the intervention or control arms of the study. Prior to random assignment, we will stratify practices based on high versus low historic prescribing rates, with the cut-point for including a clinic in the study based on the distribution of overall rates for all 3 therapeutic classes using data for 2019-2020. A primary care clinician from each clinic selected for the trial in the intervention arm (n=30 across the two ACOs) will be recruited as a clinician value champion for their clinic. They will participate in twice monthly clinician value champion training webinars for six months and then launch a 12-month initiative within their clinic to reduce PIM prescribing among PLWD. Study outcomes will be assessed 12 months after they launch their initiative.

### Sample Size and Population

Medicare beneficiaries from claims data provided by each ACO will be included in the final outcome analysis if they meet all of the following criteria prior to the start of the intervention: a) they are seen by a clinician at a participating clinic as evidenced by one or more evaluation and management claims, b) they have continuous coverage in Medicare Parts A, B and D and no months of Part C (Medicare Advantage), and c) they have two or more claims with an ICD-10 diagnosis for Alzheimer's or Alzheimer's related dementia 30 days apart or 1 inpatient stay with a principal diagnosis of Alzheimer's. We anticipate a total of approximately 5,000 patients will be included in this final analysis across both ACOs.

## **1 STUDY OBJECTIVES**

### **1.1 Primary Objective**

The Primary Outcome is medication possession rates (MPR) per quarter, for any of the 3 classes of potentially inappropriate medications. Our hypothesis is that for each medication class, the intervention will produce clinically relevant decreases in mean possession rates of 10% of a standard deviation in patients seen in intervention clinics compared to those who are seen in control group clinics.

### **1.2 Secondary Objectives**

As a secondary outcome, we will also assess the incidence of emergency department visits or hospitalizations due to a fall during the study window.

## **2 ADDITIONALLY, DATA COLLECTED THROUGH TWO INTERVIEWS WITH APPROXIMATELY 8 CLINICIAN VALUE CHAMPIONS WILL PROVIDE US WITH THE MEASURES WE NEED TO ASSESS FIVE IMPLEMENTATION OUTCOMES: APPROPRIATENESS, FIDELITY, FEASIBILITY, PENETRATION AND EQUITY.**

### **BACKGROUND AND RATIONALE**

#### **2.1 Background on Condition, Disease, or Other Primary Study Focus**

For people living with dementia (PLWD) the overuse of Potentially Inappropriate Medications (PIMs), those for which the potential for harm outweighs benefit, remains a persistent problem despite evidence-based guidelines supporting their de-adoption. A group of geriatric experts convened by the Choosing Wisely initiative identified three classes of PIMs for PLWD: antipsychotics, benzodiazepines, and hypoglycemics (sulfonylureas and insulin) with adequate glycemic control. In a systematic review the prevalence of PIMs when cognitive impairment was reported ranged from 20.6% to 80.5%. Approximately 14.3% of Medicare Part D enrollees with dementia residing in the general community are prescribed an antipsychotic. The prevalence of potentially inappropriate benzodiazepine prescriptions has been reported to be as high as 20% among elderly persons with dementia living in the community. The proportion of elderly patients with an A1c < 7% who received a prescription for sulfonylurea, insulin or combined insulin and sulfonylurea therapies was 35.2%, 24.2% and 16.3% respectively and was as prevalent in those with dementia as in those without. Park and colleagues compared rates of prescribing low-value medications in the elderly from 2006-2015 in both traditional Medicare and Medicare Advantage. Not only was there no difference in rates between the two groups, there was also no evidence of any decline in rates of prescribing over time, including use of benzodiazepines in PLWD.

#### Study Rationale

The rationale for decreasing the use of PIMs is that their use in this population of patients results in a greater likelihood of harm than benefit. Documented harms in the medical literature includes falls, worsening cognitive impairment, hospital admission, functional impairment, and death.

#### Name and Description of the Intervention:

This embedded pragmatic trial will test the effectiveness of a Clinician Value Champion on the primary outcome by randomizing primary care practices within two accountable care organizations to the intervention or control arm of the study. One clinician value champion from each clinic in the intervention arm will complete a value champion training program led by the P.I. and then implement care redesign activities in their practice to reduce the use of low value prescribing in older adults with dementia. The 6-

month training phase (months 4-9 of the study) will consist of twice monthly webinars followed by a 12-month project phase. A formative and summative evaluation of a recently completed Robert Wood Johnson funded Value Champion Fellowship program resulted in the development of a training curriculum comprised of 10 learning modules (see Table 1) for the training phase of the intervention and a project workbook to guide the value champion during the 12-month project phase. Following the 6 months of training, value champions will participate in a monthly 1-hour shared learning webinar to share successes, challenges, and brainstorm solutions for 12 months (months 10-22 of the study). We will invite former value champion fellows and faculty from the RWJF fellowship to participate in these meetings to support this new cohort of value champions.

**Table 1: Value Champion Learning Modules**

Module 1: High Value Care and Health Equity Understanding the intersection between “value” and “equity” can inform conversations between value champions, leadership and stakeholders and inform project planning.
Module 2: Engaging Leadership for High Value Care Provides participants with an overview of how to engage leadership throughout the project and provides practical tips on how to create and sustain this engagement
Module 3: So Many to Consider: Choosing an Overused Service Overuse of low-value care is common, selecting a target area of overuse requires careful consideration of multiple factors that will impact subsequent success
Module 4: How to Conduct a Stakeholder Assessment and Why it Is Important Identifying, assessing and engaging stakeholders who will be impacted by reducing the use of a service is critical to project success.
Module 5: The patient voice: engaging patient participation in your project This module explains why incorporating the patient voice is important in reducing overuse and provides examples of how to do so.
Module 6: Measurement, data and trust: Supporting change with data This module discusses common challenges and a range of solutions for collecting and reporting overuse data when taking action on overuse
Module 7: Engaging health care professionals: the Taking Action on Overuse Change Package The framework and change package provides suggested key activities to select from when designing an intervention
Module 8: Strategies Employed by Value Champions This module provides examples of intervention strategies used by clinician value champions in their setting to engage providers, staff, and patients in change efforts
Module 9: Choice Architecture and Overuse Reduction This module helps participants understand how concepts from the field of behavioral economics can be applied to their overuse reduction initiative.
Module 10: Planning for Sustainment An understanding of how value champions can incorporate plans for sustainment into every aspect of their overuse reduction initiative is provided in this module

Justification for the Intervention:

Training and supporting a clinician value champion is a simple and pragmatic approach that any health system can deploy to address overuse of PIMs in their PWLD population. They are front-line clinicians who can advocate for and influence practice-driven change and may be particularly effective in de-implementing PIMs because they can: 1) be a trusted source of information about the potential harms of PIMs, 2) provide feedback and discuss prescribing behaviors with their colleagues, 3) serve as a role model for how to

provide guideline-concordant care for PLWD, and 4) identify contextual barriers and facilitators and leverage them to reduce PIMs use in their local setting. The clinician champion model is widely recognized as effective in implementing evidence-based practices in health care settings.

